11.7. Compliance With Trial Registration and Results Posting Requirements

The sponsor of the study is solely responsible for determining whether the study and its results are subject to the requirements for submission to <https://www.clinicaltrials.gov>, <https://www.clinicaltrialsregister.eu>, or other local registries. The results of the study endpoints will be posted for the public and participants in national and local clinical trial registries such as <https://www.clinicaltrials.gov> and <https://www.japic.or.jp/> as per requirements and format from registries. Information posted will allow participants to identify potentially appropriate studies for their disease conditions and pursue participation by calling a central contact number for further information on appropriate study locations and study site contact information. These websites will not include information that can identify participants. [REDACTED]

11.8. Study and Site Closure

The sponsor or designee reserves the right to close the study site or terminate the study at any time for any reason at the sole discretion of the sponsor. Study sites will be closed upon study completion. A study site is considered closed when all required documents and study supplies have been collected and a study-site closure visit has been performed.

When the trial is completed, the investigator should inform the head of the study site of the completion in writing and submit a written summary of the trial's outcome, and then the head of the study site should promptly inform the IRB and sponsor or designee of the completion in writing.

The investigator may initiate study-site closure at any time, provided there is reasonable cause and sufficient notice is given in advance of the intended termination.

Reasons for the early closure of a study site by the sponsor or investigator may include but are not limited to:

- Failure of the investigator to comply with the Protocol, the requirements of the IRB/IEC or local health authorities, the sponsor's procedures, or GCP guidelines.
- Inadequate recruitment of participants by the investigator.
- Discontinuation of further study treatment development.

APPENDIX A. INFORMATION REGARDING EFFECTIVENESS OF CONTRACEPTIVE METHODS

For male participants in the study:
Male participants should use a condom from screening through 93 days after the end of systemic exposure. If the male participant has a partner that is of child-bearing potential, the partner should also use contraception through 93 days after the end of relevant systemic exposure. In addition, male participants must refrain from donating sperm from screening through 93 days after the end of relevant systemic exposure. Males who have had a vasectomy qualify as having met the requirement for a highly effective birth control method.
For female participants in the study:
The following methods that can achieve a failure rate of less than 1% per year when used consistently and correctly are considered as highly effective birth control methods: 
• Combined (estrogen and progestogen containing) hormonal contraception associated with inhibition of ovulation^a
– oral• Progestogen-only hormonal contraception associated with inhibition of ovulation^a
– oral– injectable– implantable^b• Intrauterine device^b• Intrauterine hormone-releasing system^b• Bilateral tubal occlusion^b• Vasectomized partner^{bc}
Acceptable birth control methods that result in a failure rate of more than 1% per year include: 
• Progestogen-only oral hormonal contraception, where inhibition of ovulation is not the primary mode of action• Male or female condom with or without spermicide^d• Cap, diaphragm, or sponge with spermicide^d• Tubal ligation

^a Hormonal contraception may be susceptible to interaction with the investigational medicinal product, which may reduce the efficacy of the contraception method.

^b Contraception methods that in the context of this guidance are considered to have low user dependency.

^c Vasectomized partner is a highly effective method of avoiding pregnancy provided that partner is the sole sexual partner of the woman of childbearing potential study participant and that the vasectomized partner has received medical assessment of the surgical success.

^d A combination of male condom with either cap, diaphragm, or sponge with spermicide (double barrier methods) are also considered acceptable, but not highly effective, birth control methods.

Source: [Clinical Trial Facilitation and Coordination Group 2014](#).

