5.1. Inclusion Criteria

Participants are eligible to be included in the study only if all of the following criteria apply:

1. Male or female Japanese participant who must be ≥ 18 years of age at the time of signing the ICF.
2. Ability to comprehend and willingness to sign a written ICF and comply with all study visits and procedures.

Note: For participants under 20 years old, those whose parent/legal guardian is willing/able to comply with study requirements and understand/sign the ICF. Participants themselves must sign the ICF form.

3. Histologically confirmed, relapsed or refractory, FL Grade 1, 2, and 3a.
4. Ineligible for HSCT.
5. Must have been treated with at least 2 prior systemic therapies for FL.
6. Radiographically measurable lymphadenopathy or extranodal lymphoid malignancy (defined as the presence of ≥ 1 lesion that measures > 1.5 cm in the LD and ≥ 1.0 cm in the LPD, respectively) as assessed by CT or MRI.
7. Participants must be willing to undergo an incisional, excisional, or core needle lymph node or tissue biopsy or provide a lymph node or tissue biopsy collected after the completion of last therapy. An earlier archived lymph node or tissue biopsy is acceptable if hospitalization is required for biopsy (eg, no superficial lymph node) and SUV_{max} by FDG-PET is < 14 .
8. ECOG performance status 0 to 2.
9. Life expectancy ≥ 12 weeks.

10. Adequate hematologic, hepatic, and renal function (values must not be achieved with growth factors):
 - a. ANC $\geq 1.0 \times 10^9/L$.
 - b. Hemoglobin ≥ 8.0 g/dL.
 - c. Platelet count $\geq 50 \times 10^9/L$.
 - d. Total bilirubin $\leq 1.5 \times ULN$. Participants with documented history of Gilbert's syndrome and in whom total bilirubin elevations are accompanied by elevated indirect bilirubin are eligible.
 - e. ALT/AST $\leq 2.5 \times ULN$ or $\leq 5 \times ULN$ in the presence of liver involvement.
 - f. Calculated creatinine clearance ≥ 40 mL/min by the Cockcroft-Gault Equation or the estimated glomerular filtration rate ≥ 40 mL/min/1.73 m² using the Modification of Diet in Renal Disease formula.
11. Willingness to avoid pregnancy or fathering children based on the criteria below:
 - a. Woman of nonchildbearing potential (ie, surgically sterile with a hysterectomy and/or bilateral oophorectomy OR ≥ 12 months of amenorrhea and > 50 years of age after cessation of all exogenous hormonal treatments).

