 - b. Woman of childbearing potential who has a negative serum pregnancy test and who agrees to take appropriate precautions to avoid pregnancy (with at least 99% certainty, see [Appendix A](#)) from screening through safety follow-up. Permitted methods that are at least 99% effective in preventing pregnancy should be communicated to the participant and their understanding confirmed.
 - c. Man who agrees to take appropriate precautions to avoid fathering children (with at least 99% certainty, see [Appendix A](#)) from screening through at least 93 days after the last dose of study treatment. Permitted methods that are at least 99% effective in preventing pregnancy should be communicated to the participant and their understanding confirmed. Participant should refrain from donating sperm from the start of the study treatment administration until 93 days after discontinuing study treatment.

Note: Approximately 18 participants with history of ASCT will be involved.

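### Appendix A labels contraceptive methods that fail more than 1% per year as acceptable for women, in conflict with the 99% requirement in criterion 11b, and leaves tubal ligation undecided

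*Protocol*

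**What the plan says.** Under Protocol Section 5.1, criterion 11b, a woman who could become pregnant must test negative on a serum test and commit to contraception. The commitment is worded "agrees to take appropriate precautions to avoid pregnancy (with at least 99% certainty, see", and the cross-reference is to the contraception appendix. It applies from the start of screening until safety follow-up ends. A further sentence of the criterion reads: "Permitted methods that are at least 99% effective in preventing pregnancy should be communicated to the participant and their understanding confirmed".

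Criterion 11a defines who does not need 11b. A woman is of nonchildbearing potential if she is "surgically sterile with a hysterectomy and/or bilateral oophorectomy", or if she is over 50 with at least 12 months of amenorrhea. Tubal surgery is not mentioned.

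Appendix A, in its part for female participants, has two lists:

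- Methods that can achieve a failure rate below 1% per year, called highly effective. "Bilateral tubal occlusion" is one of them.
- A list headed "Acceptable birth control methods that result in a failure rate of more than 1% per year include". Its four entries are a progestogen-only pill that does not work mainly by inhibiting ovulation; "Male or female condom with or without spermicide"; cap, diaphragm or sponge with spermicide; and "Tubal ligation".

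Footnote d says that a male condom combined with a cap, diaphragm or sponge is likewise acceptable, though not highly effective.

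Protocol Section 5 allows no deviations from, or waivers of, the eligibility criteria.

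**The concern.** Criterion 11b sets a threshold and names Appendix A as the place to look up what meets it. A coordinator who goes there finds a list called acceptable, made up of methods that miss the threshold, and no statement that they do not count. A site that relies on the label can enrol a woman who does not meet 11b.

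The tubal entries raise a second difficulty, because knowing the threshold does not settle them. Two sites can reach opposite decisions on the same woman while each points to a line in Appendix A. Since the protocol permits no waivers, the criterion ought to be decidable from its text.

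What is at stake is protection from exposure in pregnancy and consistent eligibility. The matter does not end with enrolment: under Protocol Section 6.7, participants without progression may stay on treatment after the end of the study, when pregnancies must still be reported.

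**Working it through.** The plan states no figure to reproduce. The check sets the criterion beside the appendix.

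**Step 1: common scale.** At least 99% effective means a failure rate of at most 100% − 99% = 1%. Criterion 11 gives no time base. Appendix A states its rates per year and draws its line at 1%, so I read the 99% as a yearly figure.

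**Step 2: apply the threshold.**

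| Appendix A group (female participants) | Failure rate by Appendix A's own wording | Meets 11b (at most 1%)? | Does Appendix A say so? |
|---|---|---|---|
| Highly effective list | below 1% per year | yes | yes, in effect |
| Acceptable list, four entries | above 1% per year | no | no |
| Double-barrier combinations, footnote d | not highly effective, so not shown to be below 1% | not shown | no |

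The heading of the acceptable list alone places all four entries outside 11b. No outside failure rates are needed.

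**Step 3: the tubal entries.** Take a premenopausal woman with a tubal ligation.

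- Criterion 11a does not cover her: she has had neither operation it names and does not meet the menopause rule. She must qualify under 11b.
- If the site matches her record to "Bilateral tubal occlusion", her method is below 1% and she qualifies.
- If the site matches it to "Tubal ligation", her method is above 1% and she does not qualify on that method.
- Appendix A defines neither term. Footnote b, attached to the occlusion entry, concerns user dependency only.

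The same woman is therefore eligible or not according to the entry chosen.

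**Step 4: number affected.** The documents plan for about 40 participants. They do not say how many are women of childbearing potential or which methods are in use, so no count can be derived.

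**The case against.** The best answer is that criterion 11 already decides the main question. It sets the 99% level and tells sites to communicate methods that reach it. Appendix A is titled as information on effectiveness, the weaker list carries its failure rate in its heading, and footnote d says the combinations are not highly effective. A site would have to overlook all of this to enrol on a condom alone. This stands, and it limits the point: a reader might infer that the protocol expressly permits methods above 1%, and it does not. What remains is a label that contradicts the rule it serves and a missing exclusion statement.

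On the tubal entries, it can be said that a record reading tubal ligation matches the entry of that name, so the literal result is the protective one. Appendix A also cites an outside guidance that may separate the terms. But a site may equally regard ligation as a form of bilateral occlusion, and the protocol itself gives it no reason not to.

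Safeguards exist. Table 4 schedules serum tests at screening, end of treatment and safety follow-up, with urine tests every 4 weeks through Week 48 and every 12 weeks after that. Sections 7.1.1 and 9.7 require a pregnant participant to stop treatment, and Section 9.7 requires reporting within 24 hours. These shorten exposure but do not prevent conception.

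A reader might also see a contradiction in criterion 11c ("Man who agrees to take appropriate precautions to avoid fathering children (with at least 99% certainty, see" Appendix A), because men are told to use a condom, which the female part places above 1%. The documents do not support that. Appendix A pairs the condom with contraception by a partner of childbearing potential, and the 99% applies to the man's precautions as a whole. The partner's method has no stated level, which is under-specification only; 11c does not require either component to reach 99% by itself.

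**Conclusion.** The point holds as a conflict between an eligibility criterion and the list meant to implement it, together with one ambiguity that careful reading cannot remove. It rests on reading 99% as a yearly figure and on the absence of any definition of the two tubal terms in the protocol.

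Its size cannot be stated. The number of women affected is unknown and could be zero. It would be tempting to attach an excess pregnancy risk, but the documents give no rates for the above-1% methods beyond that lower bound. The 16-month average participation in Table 2 includes survival follow-up, which 11b does not cover. Any multiple of the threshold would only restate assumed rates.

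The objective response rate, its confidence interval and the futility rule are unaffected. This is a participant-protection and eligibility correction, worth making at the next opportunity.

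**What to change.** In Appendix A, for female participants:

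1. Delete the above-1% list and footnote d. Alternatively, retitle both to state that these methods, used alone or as double-barrier combinations, do not satisfy criterion 11b.
2. Merge tubal ligation with bilateral tubal occlusion, or define the difference. If the list is deleted without this step, tubal ligation is no longer addressed by name.

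Criterion 11 can stay as written. At most, a sentence for non-vasectomised men could note that the condom and the partner's method together should meet the 99% in 11c.

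The cost is a few lines of Appendix A, bundled with the next amendment and its approvals (Protocol Section 11.1). There is precedent: Amendment 2 changed criterion 11c and Appendix A together for consistency. Sites would re-confirm the method for women of childbearing potential still on treatment, and a woman relying on a method that does not qualify would have to add or change one. The documents do not state whether enrolment is complete, and Amendment 4 aims at earlier closure, so the benefit may be confined to women still receiving the drug, including any who continue under Section 6.7.

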APPENDIX B. CYP3A INHIBITORS AND INDUCERS

CYP3A inhibitors or inducers may alter pascalisib concentration. These include but are not limited to the drugs listed below.

CYP3A Inhibitors

Inhibitor	Therapeutic Class
Potent CYP3A Inhibitors	
VIEKIRA PAK	Antivirals
indinavir /RIT	Protease Inhibitors
tipranavir/RIT	Protease Inhibitors
ritonavir	Protease Inhibitors
cobicistat (GS-9350)	None
ketoconazole	Antifungals
indinavir	Protease Inhibitors
troleandomycin	Antibiotics
telaprevir	Antivirals
danoprevir / RIT	Antivirals
elvitegravir / RIT	Treatments of AIDS
saquinavir / RIT	Protease Inhibitors
lopinavir / RIT	Protease Inhibitors
itraconazole	Antifungals
voriconazole	Antifungals
mibefradil	Calcium Channel Blockers
LCL161	Cancer Treatments
clarithromycin	Antibiotics
posaconazole	Antifungals
telithromycin	Antibiotics
grapefruit juice DS	Food Products
conivaptan	Diuretics
nefazodone	Antidepressants
nelfinavir	Protease Inhibitors
saquinavir	Protease Inhibitors
ribociclib	Kinase Inhibitors
idelalisib	Kinase Inhibitors
boceprevir	Antivirals

Moderate CYP3A Inhibitors	
erythromycin	Antibiotics
fluconazole	Antifungals
atazanavir / RIT	Protease Inhibitors
darunavir	Protease Inhibitors
diltiazem	Calcium Channel Blockers
darunavir / RIT	Protease Inhibitors
dronedarone	Antiarrhythmics
crizotinib	Kinase Inhibitors
atazanavir	Protease Inhibitors
letermovir	Antivirals
GSK2647544	Alzheimer's Disease & Dementia Treatments
aprepitant	Antiemetics
casopitant	Antiemetics
amprenavir	Protease Inhibitors
faldaprevir	Antivirals
imatinib	Antineoplastic Agents
verapamil	Calcium Channel Blockers
netupitant	Antiemetics
nilotinib	Kinase Inhibitors
grapefruit juice	Food Products
tofisopam	Benzodiazepines
cyclosporine	Immunosuppressants
ACT-178882	Renin Inhibitors
ciprofloxacin	Antibiotics
Magnolia vine (Schisandra sphenanthera)	Herbal Medications
isavuconazole	Antifungals
cimetidine	H-2 Receptor Antagonists
FK1706	Central Nervous System Agents

Weak CYP3A Inhibitors	
tabimorelin	Hormone Replacement
amlodipine	Calcium Channel Blockers
ranolazine	Cardiovascular Drugs
breviscapine	Herbal Medications
lomitapide	Other Antilipemics
fosaprepitant (IV)	Antiemetics
Seville orange (Citrus aurantium) juice	Food Products
amiodarone	Antiarrhythmics
diosmin	Herbal Medications
chlorzoxazone	Muscle Relaxants
M100240	Antihypertensive Agents
fluvoxamine	Antidepressants
ranitidine	H-2 Receptor Antagonists
goldenseal	Herbal Medications
clotrimazole	Antifungals
tacrolimus	Immunosuppressants
palbociclib	Kinase Inhibitors
cilostazol	Antiplatelets
ticagrelor	Antiplatelets
peppermint oil	Food Products
ivacaftor	Cystic fibrosis treatments
GSK2248761	Transcriptase Inhibitors
Guan Mai Ning	Herbal Medications
osilodrostat	Adrenal Steroidogenesis Inhibitors
AZD2327	Depression Treatments
piperine	Food Products
resveratrol	Food Products
roxithromycin	Antibiotics
suvorexant	Hypnotics - Sedatives
propiverine	Anticholinergics
isoniazid	Antibiotics
berberine	Herbal Medications
oral contraceptives	Oral contraceptives
delavirdine	NNRTIs
daclatasvir	Antivirals
simeprevir	Protease Inhibitors
atorvastatin	HMG CoA Reductase Inhibitors (Statins)

tolvaptan	Vasopressin Antagonists
almorexant	Hypnotics - Sedatives
GSK1292263	Other Antilipemics
evacetrapid	CETP inhibitors
linagliptin	Dipeptidyl Peptidase 4 Inhibitors
grazoprevir (ingredient of Zepatier)	Antivirals
lacidipine	Calcium Channel Blockers
cranberry juice	Food Products
pazopanib	Kinase Inhibitors
fostamatinib	Other
everolimus	Immunosuppressants
blueberry juice	Food Products
flibanserin	Central Nervous System Agents
lapatinib	Kinase Inhibitors
brodalumab	Immunomodulators Biologics
AMD070	Fusion Inhibitors
alprazolam	Benzodiazepines
Tong Xin Luo	Herbal Medications
glecaprevir and pibrentasvir	Antivirals
bicalutamide	Antiandrogens
sitaxentan	Endothelin Receptor Antagonists
azithromycin	Antibiotics
obeticholic acid	Miscellaneous Agents
ginkgo	Herbal Medications
teriflunomide	Other Immunomodulators

CYP3A Inducers

Inducers	Therapeutic class
Potent Inducers	
rifampin	Antibiotics
mitotane	Other Antineoplastics
avasimibe	Other Antilipemics
rifapentine	Antibiotics
apalutamide	Antiandrogens
phenytoin	Anticonvulsants
carbamazepine	Anticonvulsants
enzalutamide	Antiandrogens
St John's Wort extract	Herbal Medications
lumacaftor	Cystic Fibrosis Treatments
rifabutin	Antibiotics
phenobarbital	Anticonvulsants
Moderate Inducers	
ritonavir and St Johns wort	None
semagacestat	Alzheimer's Treatments
efavirenz	NNRTIs
tipranavir and ritonavir	Protease Inhibitors
dabrafenib	Kinase Inhibitors
lesinurad	Antigout and Uricosuric Agents
bosentan	Endothelin Receptor Antagonists
genistein	Food Products
thioridazine	Antipsychotics
nafcillin	Antibiotics
talviraline	NNRTIs
lopinavir	Protease Inhibitors
modafinil	Psychostimulants
PF-06282999	Myeloperoxidase Inactivators
etravirine	NNRTIs
lersivirine	NNRTIs
telotristat ethyl	Antidiarrheals

Weak Inducers	
eslicarbazepine	Anticonvulsants
telaprevir	Antivirals
daclatasvir and asunaprevir and beclabuvir	Antivirals
amenamevir	Antivirals
garlic	Food Products
bexarotene	Other Antineoplastics
sarilumab	Immunomodulators Biologics
artesunate and mefloquine	Antimalarials
amprenavir (fosamprenavir)	Protease Inhibitors
raltegravir	HIV-Integrase Strand Transfer Inhibitors
vemurafenib	Kinase Inhibitors
troglitazone	Thiazolidinediones
dicloxacillin	Antibiotics
sorafenib	Kinase Inhibitors
rufinamide	Anticonvulsants
sirukumab	Immunomodulators Biologics
pleconaril	Antivirals
ginseng	Herbal Medications
boceprevir	Antivirals
sulfinpyrazone	Antigout and Uricosuric Agents
ginkgo	Herbal Medications
vinblastine	Vinca Alkaloids
nevirapine	NNRTIs
armodafinil (R-modafinil)	Psychostimulants
ticagrelor	Anticoagulants and Antiplatelets
LCL161	Cancer Treatments
vicriviroc and ritonavir	Treatments of AIDS
ritonavir	Protease Inhibitors
prednisone	Corticosteroids
oxcarbazepine	Anticonvulsants
danshen	Herbal Medications
clobazam	Benzodiazepines
echinacea	Herbal Medications
ticlopidine	Anticoagulants and Antiplatelets
isavuconazole	Antifungals

brivaracetam	Anticonvulsants
Stribild	Treatments of AIDS
pioglitazone	Thiazolidinediones
VIEKIRA PAK	Antivirals
dexamethasone	Corticosteroids
terbinafine	Antifungals
quercetin	Food Products
glycyrrhizin	Herbal Medications
aprepitant	Neurokinin-1 Receptor Antagonists
pretomanib (PA-824)	Antibiotics
safinamide	MAO-B Inhibitors
oritavancin	Antibiotics
AZD 7325	Anxiolytics
methylprednisolone	Corticosteroids
topiramate	Anticonvulsants

APPENDIX C. EASTERN COOPERATIVE ONCOLOGY GROUP PERFORMANCE STATUS

Eastern Cooperative Oncology Group Performance Scores

Grade	Performance Status
0	Fully active, able to carry on all predisease performance without restriction.
1	Restricted in physically strenuous activity but ambulatory and able to carry out work of a light or sedentary nature, eg, light house work, office work.
2	Ambulatory and capable of all self-care but unable to carry out any work activities. Up and about more than 50% of waking hours.
3	Capable of only limited self-care, confined to bed or chair more than 50% of waking hours.
4	Completely disabled. Cannot carry on any self-care. Totally confined to bed or chair.
5	Dead.

Source: [Oken et al 1982](#).

APPENDIX D. LUGANO CLASSIFICATION FOR RESPONSE ASSESSMENT (CT-BASED ONLY)

Site	CT-Based Response
	Complete radiologic response (all of the following)
Lymph nodes and extralymphatic sites	Target nodes/nodal masses must regress to ≤ 1.5 cm in LDi.
Nonmeasured lesion	Absent.
Organ enlargement	Regress to normal.
New lesions	None.
Bone marrow	Normal by morphology; if indeterminate, immunohistochemistry negative.
	Partial remission (all of the following)
Lymph nodes and extralymphatic sites	
 • $\geq 50\%$ decrease in SPD of up to 6 target measurable nodes and extranodal sites. • When a lesion is too small to measure on CT, assign 5 mm \times 5 mm as the default. • When no longer visible, 0 \times 0 mm. For a node > 5 mm \times 5 mm but smaller than normal, use actual measurement.
Nonmeasured lesions	Absent/regressed, but no increase.
Organ enlargement	Spleen must have regressed by $> 50\%$ in length beyond normal.
New lesions	None.
Bone marrow	Not applicable.
	Stable disease
Target nodes/nodal masses, extranodal lesions	$< 50\%$ decrease from baseline in SPD of up to 6 dominant, measurable nodes and extranodal sites; no criteria for PD are met.
Nonmeasured lesions	No increase consistent with progression.
Organ enlargement	No increase consistent with progression.
New lesions	None.
Bone marrow	Not applicable.

Site	CT-Based Response
	Progressive disease (requires at least 1 of the following)
Individual target nodes/nodal lesions	
PPD progression:
 
 • An individual node/lesion must be abnormal with all of the following: 
 - LDi > 1.5 cm. - Increase by $\geq 50\%$ from PPD nadir. - Increase in LDi or SDi from nadir: 
 o 0.5 cm for lesions ≤ 2 cm. o 1.0 cm for lesions > 2 cm. • In the setting of splenomegaly, the splenic length must increase by > 50% of the extent of its prior increase beyond baseline (eg, a 15 cm spleen must increase to > 16 cm). If no prior splenomegaly, must increase by at least 2 cm from baseline. • New or recurrent splenomegaly. • New or clear progression of pre-existing nonmeasured lesions. • Regrowth of any previously resolved lesions. • A new node > 1.5 cm in any axis. • A new extranodal site > 1.0 cm in any axis; if < 1.0 cm in any axis, its presence must be unequivocal and must be attributable to lymphoma. • Assessable disease of any size unequivocally attributable to lymphoma. • New or recurrent involvement of the bone marrow.

CT = computed tomography; EOT = end of treatment; LDi = longest transverse diameter of lesion; MRI = magnetic resonance imaging; PPD = cross-product of the longest transverse diameter and perpendicular diameter; SDi = shortest axis perpendicular to the longest transverse diameter; SPD = sum of the product of the perpendicular diameters for multiple lesions.

